8.2.2.6 Adverse events (AEs)

After informed consent is obtained, AEs will be recorded continuously through the study conduct, and managed as outlined in Section 9 and according to the Safety Management Plan developed for this study. Events that occur prior to initiation of study treatment will be assessed as “not related” to study medication; AEs that occur after the first administration of study medication will be assessed as treatment-emergent AEs (TEAEs).

Adverse events will be categorised based on severity; relationship to study treatment and seriousness and according to National Cancer Institute's Common Terminology Criteria for Adverse Events (NCI CTCAE) Version 5.0.

8.2.3 Efficacy Assessments

8.2.3.1 Relapse

Any of the following events will be considered as relapse: loco-regional recurrence (as defined in Section 3.3.1), distant metastases, death from same cancer or death from other cancer, non-cancer-related death, and treatment-related death.

A positive CT/MRI/PET scan (appearance of a lesion) will be considered evidence of relapse. Two consecutive increases in CEA levels above upper limit level (time gap decided by the clinical investigator).

Confirmation of progression guidelines are set for the following reasons:

- for patient management and treatment decisions
- in the absence of significant clinical deterioration, to promote the collection of additional scans after the first radiologic RECIST 1.1 assessment of progressive disease (PD) in order to distinguish pseudoprogression from true radiologic progression, also known as RECIST 1.1 modified for confirmation of progression
- when scans are evaluated by Investigator and by BICR, to reduce informative censoring by Investigator assessments (Investigator assesses PD at a time-point earlier than does BICR).

Confirmed objective disease progression refers to either of the following scenarios: 1. clinical progression/deterioration followed by a radiologic verification scan (PD by RECIST 1.1); or 2. in the absence of significant clinical deterioration, radiologic PD by RECIST 1.1 followed by a second radiologic confirmation scan with PD assessed according to the specific confirmation of progression criteria listed below. RECIST 1.1 modified for confirmation of progression refers to the second scenario above. The confirmatory scan should occur preferably at the next scheduled imaging visit and no earlier than 4 weeks following the date of the immediate prior assessment of RECIST 1.1 PD.

Immediate prior radiologic progression would be considered confirmed if any the following criteria are met in the confirmatory scan:

- $\geq 20\%$ increase in the sum diameters of target lesions (TLs) compared with the nadir at 2 consecutive visits, with an absolute increase of at least 5 mm in sum of diameters compared to nadir,
- and/or significant progression (worsening) of non-target lesions (NTLs) and/or of pre-existing new lesions at the confirmatory scan time-point

compared with the immediate prior time-point (Note: Pre-existing new lesions are evaluated as NTLs at the confirmatory scan time-point),

- and/or additional new unequivocal lesions at the confirmatory scan time-point.

NOTE: In order to have confirmed objective disease progression, there should be two consecutive assessments meeting the PD definition: the first PD by RECIST 1.1 and the second PD using the confirmation of progression criteria (above). If the first assessment fulfilling the PD definition by RECIST 1.1 is not confirmed, continue with assessments until the next PD by RECIST 1.1, which in turn will need its own immediate subsequent confirmation scan. In the absence of significant clinical deterioration, treatment with study drug may continue between the initial assessment of progression and the scan to confirm progression.

If the confirmation scan confirms progression, then the date of the prior scan with PD should be declared as the date of progression.

If progression is not confirmed, in the absence of significant clinical deterioration, then the patient should continue study drug and on-treatment assessments until the next PD which will also require a follow-up confirmation scan. If the first PD is not confirmed by the immediate next scan, then the Investigator should not change the PD assessment of the first scan.

If a patient discontinues treatment (and/or receives a subsequent anticancer therapy) prior to radiologic progression, then the patient should still continue to be followed until confirmed objective disease progression.

8.2.3.2 Carcinoembryonic antigen and CA 19-9

Blood will be collected for assessment of CEA and CA 19-9 as markers of potential relapse of CRC. Samples will be analysed at the local laboratory.

Data from CEA and CA 19-9 analyses done at any times other than those specified for this study, i.e., done as part of SoC of the facility, will be collected for the eCRF.

8.2.3.3 Computed tomography and magnetic resonance imaging

CT/MRI/PET scans will be done to detect relapse, as specified by the objectives and endpoints of the study, and to confirm a diagnosis of relapse at any time during the study (Section 3.3.1).

While scans will be done as per SoC of the facility, minimal standards for CT/MRI/PET procedures will be provided. Data from CT/MRI/PET scans done at any times other than those specified for this study, i.e., done as part of SoC of the facility, will be collected for the eCRF.

8.3 Appropriateness of Measurements

All measurements will be carried out according to standard methodologies and to ensure patient safety. The methods used in this study are commonly regarded as reliable and valid, and relevant to the indication. The design of this study is a design for the assessment of efficacy, safety, and tolerability in a Phase IIb study, including use of the ECOG Performance Scale. CT/MRI/PET scans and CEA/CA 19-9 have been included for the purposes of this study and the timing is that patients would be undergoing CT/MRI/PET scans and CEA/CA 19-9 as part of SoC treatment and follow-up of NED CRC patients.

9 ADVERSE EVENT ASSESSMENTS

The criteria outlined in this section will be used to evaluate each patient before, during, and after treatment to determine the safety associated with the patient's treatment and study procedures. The safety of the investigational treatments will be assessed by evaluating the nature and frequency of Adverse Events (AEs). Details of the management of Serious Adverse Events (SAEs) will be further documented in the Safety Management Plan developed for this study.

Clinical laboratory tests

Clinical laboratory safety tests, including serum pregnancy tests, will be performed in a licensed clinical laboratory according to local standard procedures. Sample tubes and sample sizes may vary depending on the laboratory method used and routine practice at the site. Pregnancy tests may be performed at the site using a licensed test (urine or serum pregnancy test). Abnormal clinically significant laboratory results should be repeated as soon as possible (preferably within 24 to 48 hours).

Other safety assessments

If new or worsening pulmonary symptoms (e.g., dyspnea) or radiological abnormality suggestive of pneumonitis/ILD is observed, toxicity management as described in detail in the Dosing Modification and Toxicity Management Guidelines (see Appendix 1) will be applied. The results of the full diagnostic workup (including high-resolution computed tomography [HRCT], blood and sputum culture, hematological parameters, etc.) will be captured in the eCRF. It is strongly recommended to perform a full diagnostic workup, to exclude alternative causes such as lymphangitic carcinomatosis, infection, allergy, cardiogenic edema, or pulmonary hemorrhage. In the presence of confirmatory HRCT scans where other causes of respiratory symptoms have been excluded, a diagnosis of pneumonitis (ILD) should be considered and the Dosing Modification and Toxicity Management Guidelines should be followed.

The Principal Investigator is responsible for ensuring that all staff involved in the study is familiar with the content of this section.

9.1 Definitions

9.1.1 Adverse Events (AEs)

According to the International Conference of Harmonization (ICH), an AE is any untoward medical occurrence in a clinical investigation subject (patient) administered a pharmaceutical product and which does not necessarily have a causal relationship with this treatment. An AE can therefore be any unfavorable and unintended sign (including an abnormal laboratory finding), symptom, or disease temporally associated with the use of a medicinal (investigational) product, whether or not considered related to the investigational product. Pre-existing conditions which worsen during a study are to be considered as AEs.

An AE that occurs after signing informed consent but prior to the first administration of study treatment will be considered not related to study treatment.

9.1.2 Definition of adverse events of special interest (AESI)

An adverse event of special interest (AESI) is one of scientific and medical interest specific to understanding of the Investigational Product and may require close monitoring. An AESI may be serious or non-serious.

If the Investigator has any questions in regards to an event being an imAE, the Investigator should promptly contact the Study Physician.

AESIs observed with durvalumab include:

- Diarrhea / Colitis and intestinal perforation
- Pneumonitis / ILD
- Hepatitis / transaminase increases
- Endocrinopathies (i.e. events of hypophysitis/hypopituitarism, adrenal insufficiency, hyper- and hypothyroidism and type I diabetes mellitus)
- Rash / Dermatitis
- Nephritis / Blood creatinine increases
- Pancreatitis / serum lipase and amylase increases
- Myocarditis
- Myositis / Polymyositis
- Neuropathy / neuromuscular toxicity (e.g. Guillain-Barré, and myasthenia gravis)
- Intestinal Perforations

Other inflammatory responses that are rare/less frequent with a potential immune-mediated etiology include, but are not limited to:

- Pericarditis
- Sarcoidosis
- Uveitis
- Other events involving the eye and skin
- Hematological events
- Rheumatological events
- Vasculitis
- Non-infectious meningitis
- Non-infectious encephalitis.

It is possible that events with an inflammatory or immune mediated mechanism could occur in nearly all organs.

In addition, infusion-related reactions and hypersensitivity/anaphylactic reactions with a different underlying pharmacological aetiology are also considered AEsIs.

Further information on these risks (e.g. presenting symptoms) can be found in the current version of the durvalumab Investigator's Brochure. More specific guidelines for their evaluation and treatment are described in detail in the Dosing Modification and Toxicity Management Guidelines (please see Appendix 1). These guidelines have been prepared by the Sponsor to assist the Investigator in the exercise of his/her clinical judgment in treating these types of toxicities. These guidelines apply to AEs considered causally related to the study drug/study regimen by the reporting investigator.

9.1.3 Serious Adverse Event (SAEs)

A SAE is any experience that suggests a significant hazard, contraindication, side effect or precaution. It is any AE that at any dose fulfils at least one of the following criteria:

- ✓ is fatal (results in death)¹ ;
- ✓ is Life-Threatening² ;
- ✓ required in-patient hospitalization or prolongation of existing hospitalization;
- ✓ results in persistent or significant disability/incapacity;
- ✓ is a congenital anomaly/birth defect;
- ✓ is medically significant or requires intervention to prevent one or other of the outcomes listed above. Medical or scientific judgment should be exercised in deciding whether expedited reporting is appropriate in this situation. Examples of medically important events are intensive treatment in an emergency room or at home for allergic bronchospasm, blood dyscrasias, or convulsions that do not result in hospitalizations; or development of drug dependency or drug abuse.

Adverse Events (AEs) for malignant tumours reported during a study should generally be assessed as Serious AEs. If no other seriousness criteria apply, the 'Important Medical Event' criterion should be used. In certain situations, however, medical judgement on an individual event basis should be applied to clarify that the malignant tumour event should be assessed and reported as a Non-Serious AE. For example, if the tumour is included as medical history and progression

¹ Death is an outcome, not an event. The term sudden death should be used only when the cause is of a cardiac origin as per standard definition. The terms death and sudden death are clearly distinct and must not be used interchangeably.

² the term "Life-Threatening" refers to an event in which the patient was at immediate risk of death at the time of the event; it does not refer to an event which could hypothetically have caused a death if had it been more severe

occurs during the study, but the progression does not change treatment and/or prognosis of the malignant tumour, the AE may not fulfill the attributes for being assessed as Serious, although reporting of the progression of the malignant tumor as an AE is valid and should occur. Also, some types of malignant tumours, which do not spread remotely after a routine treatment that does not require hospitalization, may be assessed as Non-Serious; examples include Stage 1 basal cell carcinoma and Stage 1A1 cervical cancer removed via cone biopsy.

The above instruction applies only when the malignant tumour event in question is a new malignant tumour (i.e., it is not the tumour for which entry into the study is a criterion and that is being treated by the IP under study and is not the development of new or progression of existing metastasis to the tumour under study). Malignant tumours that – as part of normal, if rare, progression – undergo transformation (e.g., Richter's transformation of B cell chronic lymphocytic leukemia into diffuse large B cell lymphoma) should not be considered a new malignant tumour.

Hospitalisation will **not be considered a SAE** for the following cases:

- hospitalisation or prolongation of hospitalisation for a procedure required by the study Protocol
- hospitalisation or prolongation of hospitalisation is part of a routine procedure followed by the study site
- hospitalisations or prolongation of hospitalisation due to merely diagnostic reasons, planned surgery, planned chemotherapy.

Merely the introduction of a patient in the emergency room does not fulfil the criteria “hospitalisation” without subsequent admission.

Medical and scientific judgment should be exercised in deciding whether SAE reporting is appropriate in other situations, such as important medical events that are not immediately life-threatening or do not result in death or hospitalisation.

9.1.4 Adverse Drug Reaction (ADR)

All AE related to the medicinal (investigational) product at any dose should be an ADR.

An ADR, the nature or severity of which is not consistent with the applicable product information is an Unexpected adverse drug reaction.

9.1.5 Suspected Unexpected Serious Adverse Reaction (SUSAR)

When an SAE is recognized as unexpected and its correlation with the investigational product cannot reasonably be excluded, it is classified as Suspected Unexpected Serious Adverse Reaction (SUSAR).

9.1.6 Classification of AEs

ALL AE will be classified on the basis of its intensity and relatedness to study treatments. The relationship between an AE and the study treatments will be determined by the Investigator on the basis of his or her clinical judgment and the following definitions:

9.1.6.1 Intensity

Intensity of all AEs will be graded according to the NCI Common Terminology Criteria for Adverse Events v 5.0 (CTCAE v 5.0; most recent sub-version), on a five-point scale (Grade 1 to 5) and reported in detail on the CRF.

AEs not listed on the CTCAE should be graded as follows:

Table 6. Grading of AEs not listed on the CTCAE

CTC Grade Equivalent to:	
Grade 1 (Mild)	Mild Discomfort noticed but no disruption of normal daily activity
Grade 2 (Moderate)	Moderate Discomfort sufficient to reduce or affect daily activity; no treatment or medical intervention is indicated although this could improve the overall well-being or symptoms of the patient
Grade 3 (Severe)	Severe Inability to work or perform normal daily activity; treatment or medical intervention is indicated in order to improve the overall wellbeing or symptoms; delaying the onset of treatment is not putting the survival of the patient at direct risk
Grade 4 (Life threatening)	Life threatening/disabling. An immediate threat to life or leading to a permanent mental or physical conditions that prevents work or performing normal daily activities; treatment or medical intervention is required in order to maintain survival
Grade 5 (Death)	AE resulting in death

9.1.7 Trial Relationship to Study Drug

The investigator will evaluate the relationship of the adverse events to the study product based on the following definitions:

Table 7. AEs Relatedness to the study chemotherapy

Definite/Certain (yes)	are terms applied to an adverse events which have a timely relationship to the study drug and no alternative etiology is present. The adverse event must have occurred within a reasonable temporal sequence of the chemotherapy administration, must not be reasonably explained, and must follow a known pattern of response
Probable (yes)	means that the adverse event has a timely relation to the study drug and a potential alternative etiology is not apparent (i.e., fever or malaise when no other symptoms suggestive of an illness are present)
Possible (yes)	means that the adverse event has a timely relation to the study drug; however, a potential alternative etiology exists, which may be responsible for the symptom (i.e., fever or malaise when other symptoms are present that suggest another etiology such as upper respiratory infection)
Unrelated/Unlikely (No)	means that the adverse event is applied to those adverse events for which evidence exists that the symptom is definitely related to an etiology other than the study drug (i.e., car accident, or a symptom suggestive of another illness that is not accepted to have a possible relatedness to chemotherapy).

9.1.8 Follow-up of Adverse Event

The Investigator must continue to monitor the following events until they resolve or until the Investigator assesses them as chronic or stable: 1) all SAEs; 2) any non-serious events assessed as possibly, probably, or definitely related to the study treatment; and 3) any SAEs or AEs that lead to study withdrawal. This follow up will be extended through the end of the study.

9.1.9 Follow-up of Abnormal Laboratory Test Values

In the event of medically significant unexplained abnormal laboratory test values, the tests should be repeated and followed up until they have returned to the normal range and/or an adequate explanation of the abnormality is found. If a clear explanation is established it should be recorded on the CRF.

9.2 Reporting of Adverse Events

AEs: At each study visit the Investigator, will determine whether any AEs have occurred. Any AEs will be reported in the patient's medical record and on the AE eCRF page and each will be classified according to the criteria above. Adverse event reporting for each patient starts when the patient signs the Informed Consent

Form (ICF). Any pre-existing conditions that are detected as part of the initial pre-randomization procedures will need to be reported in the medical history and not as an AE. However, pre-existing conditions that worsen after enrolment should be reported as an AE.

SAEs: AEs and SAEs will be collected from the time of the patient signing the informed consent form until the follow-up period is completed (90 days after the last dose of durvalumab). If an event that starts post the defined safety follow up period noted above is considered to be due to a late onset toxicity to study drug then it should be reported as an AE or SAE as applicable.

During the course of the study, all AEs and SAEs should be proactively followed up for each patient for as long as the event is ongoing. Every effort should be made to obtain a resolution for all events, even if the events continue after the patient has discontinued study drug or the study has completed.

The Sponsor retains the right to request additional information for any patient with ongoing AE(s)/SAE(s) at the end of the study, if judged necessary.

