Tumor imaging/ response assessments ^c	X	X		X
Hematology ^d	X	X		X
Chemistry ^d	X	X		X
Biomarkers ^d	X	X		X
AEs assessments	X	X	X	X
Survival and anti-cancer therapy			X	X

Abbreviation: CBC: cell blood count; RBC: red blood cell; WBC: White blood cell; aPTT: activated partial thromboplastin time; PT: prothrombin time; INR: international normalized ratio; AST: Aspartate aminotransferase; ALT: alanine aminotransferase; LDH: Lactate dehydrogenase; β -hCG: beta-human chorionic gonadotropin; Na: sodium; K: potassium; Cl: chloride; Mg: magnesium; Ca: calcium; P: phosphate; CEA: Carcinoembryonic antigen; Ca 19-9: Carbohydrate antigen 19-9; ECOG PS: Eastern Cooperative Oncology Group Performance Status; ECG: electrocardiogram; AEs: adverse events

a) Vital signs and Physical examination

Patients will have a complete physical exam to include an examination of major body systems and an assessment for emergent toxicities or changes from prior visits. Limited physical examination should be performed symptom-directed.

Examinations will be conducted by a physician, trained physician's assistant, or nurse practitioner, as acceptable according to local regulation.

Vital signs include: blood pressure and heart rate, body temperature, respiratory rate.

b) Electrocardiogram (ECG)

Perform a 12-lead resting electrocardiogram (ECG) before the beginning of the treatment, at the end-of-treatment and if clinically indicated. Patients should be in a supine position for at least 10 min before recording. ECG tracings will be reviewed by a qualified physician for assessment of QT interval as well as signs of qualitative abnormalities, including evaluation of rhythm, ST segment morphology, T wave morphology, and presence/absence of U wave.

The original ECG tracing will be maintained in the source documentation of each patient.

c) Tumor imaging/ response assessments

Including computed tomography (CT) scan / magnetic resonance imaging (MRI) / PET scan. The same radiographic procedure should be used throughout the study for each patient.

Tumor assessment should be performed every 12 weeks \pm 1 week for the first year (relative to the date of randomization), every 16 \pm 1 week in the second year and then every 24 weeks \pm 1 week thereafter until RECIST 1.1-defined radiological PD or death (whichever comes first).

d) Local laboratory assessments will include the following:

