6.2 Inclusion Criteria

To be enrolled in this study each patient must meet all of the following criteria at the time of randomization:

1. Signed ICF, after oral as well as written information. Capable of giving signed informed consent which includes compliance with the requirements and restrictions listed in the informed consent form (ICF) and in this protocol. Written informed consent obtained from the patient/legal representative prior to performing any protocol-related procedures, including screening evaluations
2. Age ≥ 18 years at time of study entry
3. Body weight >30 kg
4. Histologically confirmed diagnosis of colorectal adenocarcinoma;
5. Patients must be in NED after completion of any treatments for stage IV CRC, including resections, RFA; RT with or without neoadjuvant/adjuvant therapies or CR after chemotherapy;
6. Patients must be randomized within 10 weeks since the achievement of the NED state. Those who have also received adjuvant therapy following the locoregional treatment are still eligible, provided they are randomized within 4 weeks since the last chemotherapy cycle;
7. NED state ascertained by means of CT scan and/or PET scan and/or MRI scan;
8. ECOG Performance Status ≤ 1 ;
9. Life expectancy of at least 12 weeks
10. CEA within normal limits;
11. No residual toxicity from previous chemotherapy;
12. Women of childbearing potential must use safe contraception.
13. Adequate normal organ and marrow function as defined below:

Haemoglobin ≥ 9.0 g/dL

Absolute neutrophil count (ANC) $\geq 1.5 \times 10^9$ /L

- Platelet count $\geq 100 \times 10^9$ /L

Serum bilirubin ≤ 1.5 x institutional upper limit of normal (ULN).

This will not apply to patients with confirmed Gilbert's syndrome (persistent or recurrent hyperbilirubinemia that is predominantly unconjugated in the absence of haemolysis or hepatic pathology), who will be allowed only in consultation with their physician.

Serum Creatinine $\leq 1.5 \times \text{ULN}$ or measured creatinine clearance (CL) $>40 \text{ mL/min}$ or Calculated creatinine CL $>40 \text{ mL/min}$ by the Cockcroft-Gault formula (Cockcroft and Gault 1976) or by 24-hour urine collection for determination of creatinine clearance:

Males:

$$\text{Creatinine CL (mL/min)} = \frac{\text{Weight (kg)} \times (140 - \text{Age})}{72 \times \text{serum creatinine (mg/dL)}}$$

Females:

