19. Female patients who are pregnant or breastfeeding or male or female patients of reproductive potential who are not willing to employ effective birth control from screening to 90 days after the last dose of durvalumab monotherapy.
20. Known allergy or hypersensitivity to any of the study drugs or any of the study drug excipients.
21. Any condition that, in the opinion of the investigator, would interfere with evaluation of the study drug or interpretation of patient safety or study results.

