7.2 Dose interruption or reduction

In case of adverse events, dose interruption or reduction are at the investigator's discretion based on local clinical practice.

If an adverse event is attributed to only one drug (i.e., regorafenib or durvalumab), the investigator's discretion will be used to determine what drug dose should be reduced or withheld.

Table 5. Dose reduction levels

Drug	Dose levels		
	Starting dose	-1	-2
Durvalumab	1500mg	-	-
Regorafenib	90mg	60 mg	30 mg

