8.1.3 End of treatment

End of treatment is defined as the last planned dosing visit within the 12-month dosing period. For patients who discontinue durvalumab prior to 12 months, end of treatment is considered the last visit where the decision is made to discontinue treatment. All required procedures may be completed within \pm 7 days of the end of

treatment visit. Repeat disease assessment is not required if performed within 28 days prior to the end of treatment visit.

Assessments for patients who have completed the treatment and achieved disease control, or have discontinued durvalumab due to toxicity in the absence of confirmed progressive disease:

1. Prior/concomitant medications
2. Complete physical examination
3. Vital signs
4. ECOG performance status
5. 12 - lead ECG
6. Tumor imaging/response assessment
7. Clinical chemistry and haematology (CBC + differential platelet count; creatinine; total bilirubin; AST; ALT; alkaline phosphatase; LDH; albumin; glucose; potassium; sodium; calcium)
8. Documentation of AEs/SAEs

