
Grade 1 No dose modification
	

Grade 2 Hold study drug/study regimen dose until Grade 2 resolution to Grade ≤ 1.
 
If toxicity worsens, then treat as Grade 3 or Grade 4.
 
Study drug/study regimen can be resumed once event stabilizes to Grade ≤ 1 after completion of steroid taper.
 
Patients with endocrinopathies who may require prolonged or continued steroid replacement can be retreated with study drug/study regimen on the following conditions:
 
 1. The event stabilizes and is controlled. 2. The patient is clinically stable as per Investigator or treating physician's clinical judgement. 3. Doses of prednisone are at ≤ 10 mg/day or equivalent. 	

Grade 3 Depending on the individual toxicity, study drug/study regimen may be permanently discontinued. Please refer to guidelines below.
	

Grade 4 Permanently discontinue study drug/study regimen.
	

Dosing Modification and Toxicity Management Guidelines for Immune-Mediated, Infusion-Related, and Non-Immune-Mediated Reactions 17 October 2019 Version (CTCAE v5.0)

General Considerations regarding Immune-Mediated Reactions

Dose Modifications

Note: For asymptomatic amylase or lipase levels of >2X ULN, hold study drug/study regimen, and if complete work up shows no evidence of pancreatitis, study drug/study regimen may be continued or resumed.

Note: Study drug/study regimen should be permanently discontinued in Grade 3 events with high likelihood for morbidity and/or mortality – e.g., myocarditis, or other similar events even if they are not currently noted in the guidelines.

Similarly, consider whether study drug/study regimen should be permanently discontinued in Grade 2 events with high likelihood for morbidity and/or mortality – e.g., myocarditis, or other similar events even if they are not currently noted in the guidelines – when they do not rapidly improve to Grade <1 upon treatment with systemic steroids and following full taper

Note: There are some exceptions to permanent discontinuation of study drug for Grade 4 events (i.e., hyperthyroidism, hypothyroidism, Type 1 diabetes mellitus).

Toxicity Management

- With long-term steroid and other immunosuppressive use, consider need for *Pneumocystis jirovecii* pneumonia (PJP, formerly known as *Pneumocystis carinii* pneumonia) prophylaxis, gastrointestinal protection, and glucose monitoring.

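### The AE/SAE window (9.2), early end of treatment (8.1.3) and contraception period (exclusion 19) are tied to durvalumab alone in a two-drug regimen: a minor safety-wording correction

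*Combined protocol and SAP*

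**What the plan says.** Section 7.1 gives the experimental arm regorafenib on days 1 to 21 of each 28-day cycle and durvalumab every four weeks, both for up to one year. Section 7.3.1 caps durvalumab at 12 doses.

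Three rules refer to durvalumab without regorafenib:

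- Section 9.2 runs AE and SAE collection from consent "until the follow-up period is completed (90 days after the last dose of durvalumab". Later events are reportable if judged to be late-onset toxicity of study drug.
- Section 8.1.3 states: "For patients who discontinue durvalumab prior to 12 months, end of treatment is considered the last visit" at which the decision to stop is made.
- Exclusion 19 (section 6.3, repeated in the synopsis) requires willingness to use effective birth control "from screening to 90 days after the last dose of durvalumab monotherapy". Inclusion 12 adds "Women of childbearing potential must use safe contraception", for women only and with no end date.

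On separating the two drugs, section 7.2 says that when an event is attributed to one of them, investigator discretion "will be used to determine what drug dose should be reduced or withheld". Section 6.4.1 is headed as permanent discontinuation of durvalumab or regorafenib. For the more severe immune-mediated events Appendix 3 says "Permanently discontinue study drug/study regimen", without saying whether that means one drug or both.

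Other parts of the protocol use drug-neutral wording. Sections 8.2.1.3 and 9.8 follow or report pregnancies up to 6 months after study treatment or study medication. Table 2 has an AE assessment 30 days after last treatment or at the start of other anticancer therapy.

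**The concern.** A safety window in a combination arm should run from whichever component is taken last. Here the clock starts at the last infusion, although regorafenib tablets continue for 20 days after each infusion day. The stated 90 days is therefore shorter when counted from the second drug. If the drugs were stopped at different times, the shortfall could grow until the window closed during dosing.

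What could be lost or recorded unevenly between sites is mainly non-serious AEs that are not attributed to study drug and that start after the window. The contraception period could end sooner after regorafenib than after durvalumab, or in the conditional case during regorafenib dosing. The word *monotherapy* adds a separate problem: read literally, exclusion 19 refers to a treatment that nobody in the trial receives.

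**Working it through.** The plan states no figure to reproduce here. The check is day arithmetic from the stated schedule, taking day 1 as cycle 1 day 1 and assuming 28-day cycles without delays.

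**Inputs.** Durvalumab on day 1 of each cycle, up to 12 doses (7.1, 7.3.1). Regorafenib on days 1 to 21 of each cycle, taken as 12 cycles (7.1 and synopsis). Window of 90 days after the last durvalumab dose (9.2, exclusion 19).

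**Full course (no further assumption).**

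- Last durvalumab: 11 × 28 + 1 = day 309.
- Last regorafenib: 11 × 28 + 21 = day 329.
- Window as written closes: 309 + 90 = day 399.
- Time after the last tablet: 399 − 329 = 70 days.
- Window counted from the later drug: 329 + 90 = day 419, which is 419 − 399 = 20 days longer.

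**Conditional case: durvalumab stops after cycle k and regorafenib continues alone to day 329.**

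- Last durvalumab: day 28(k − 1) + 1. Window closes: day 28(k − 1) + 91.
- The window closes before day 329 when k is 9 or less (k = 9 gives day 315; k = 10 gives day 343).
- Total regorafenib dosing days: 12 × 21 = 252.
- Dosing days after closure, for k ≤ 9: 14 + 21 × (9 − k).

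| Last durvalumab cycle | Window closes (day) | Regorafenib dosing days after closure |
|---|---|---|
| 1 | 91 | 182 of 252 (72%) |
| 3 | 147 | 140 (56%) |
| 6 | 231 | 77 (31%) |
| 9 | 315 | 14 (6%) |
| 10 to 12 | 343 to 399 | 0 |

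These figures show how far the wording could stretch in one patient. They are not an estimate of what will happen, because the documents do not say how many patients, if any, would be in this position.

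**Section 8.1.3.** No interval is counted from durvalumab here; stopping durvalumab is the trigger. Read one way, stopping it ends treatment with both drugs, and then there is no gap during dosing. Read with 7.2 and the heading of 6.4.1, regorafenib might continue, and then end of treatment would be declared while a study drug was still being taken. The text does not settle which reading applies.

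**The case against.** The strongest reply is that little depends on the 9.2 end date, and most of that reply stands.

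**Experimental arm.** AEs are documented at every on-treatment visit (8.1.2, Table 2) and again 30 days after last treatment, counted from treatment and not from durvalumab. Section 9.6 requires all SAEs from enrolment, whatever the causality, and states no end date. The late-onset clause in 9.2 refers to study drug and so covers regorafenib. After a full course 70 days remain, and nothing in the documents says that regorafenib needs 90.

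**Regorafenib alone.** A reader might infer from the table above that up to 72% of dosing days will go unmonitored. The documents do not support that. No section states that regorafenib may continue after a permanent durvalumab stop, section 7.2 speaks only of reducing or withholding, and visits and laboratory tests required for dosing (section 8) would still apply.

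**Controls.** A reader might also infer that controls who never receive durvalumab have no AE collection, because 9.2 yields no end date for them. That goes too far. Section 8.1.2 documents AEs and SAEs every 12 weeks, section 8.1.4 continues safety assessments in follow-up, and Table 3 lists "AEs assessments" at visits and in follow-up. Nor is an effect on the toxicity comparison shown: section 5.2.4 uses the worst grade over the treatment period, in a safety population (5.1) that requires at least one dose of study drug.

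**Conflict with 8.2.2.6.** That section says "AEs will be recorded continuously through the study conduct", which looks incompatible with a 90-day stop. The same sentence defers to Section 9 and to a Safety Management Plan that is not in the supplied text and may set the cut-offs. Uneven site practice therefore cannot be established.

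**Contraception.** Exclusion 19 is an entry criterion, and the consent pages are not available here, so it cannot be said that men get no other instruction. Pregnancy reporting already runs 6 months from study treatment or medication, and 9.8 also covers partners of male patients.

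What survives is the wording: three stated rules name one drug of two, and one of them names a regimen that the trial does not use.

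**Conclusion.** The point holds as a minor safety-reporting correction. Sections 9.2 and 8.1.3 and exclusion 19 are tied to durvalumab alone in a durvalumab-plus-regorafenib arm, and *monotherapy* in exclusion 19 is wrong for this trial.

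The certain size is 20 days: after a full course without delays, the 9.2 and exclusion 19 windows end 70 days after the last regorafenib tablet, not 90. Closure during regorafenib dosing needs two conditions, durvalumab stopped at cycle 9 or earlier and regorafenib continued alone; the protocol neither allows nor excludes this, and it may affect no patients. Efficacy, alpha and power are unaffected.

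**What to change.** - In 9.2 and in exclusion 19 with its synopsis copy, count the 90 days from the last dose of durvalumab or regorafenib, whichever is later.
- In exclusion 19 and the synopsis copy, delete *monotherapy*.
- In 8.1.3, define early end of treatment by the later of the two drugs to be stopped, not by durvalumab alone.

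The cost is a wording amendment in three sections and the synopsis, and slightly more AE data entry (20 more days of collection after a full course). Sample size, alpha and power do not change.
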